1.6. DATABASE LOCK

Approximately 4 months after enrollment of the last patient, once the targeted 209 PFS events are observed, database interim lock will be conducted. The primary PFS analyses will be performed including analyses of efficacy and safety data. A clinical study report (CSR) will be prepared after the primary PFS analyses.

The final analysis will be performed at the end of the study after all patients have completed the follow-up period with database final lock.

1.7. MODIFICATIONS TO THE STATISTICAL SECTION OF THE PROTOCOL

The current SAP is based on Protocol v9.0 dated 21 May 2020.

The following endpoints will not be analyzed as the corresponding data are not available. All endpoints correspond to Phase 2 and Phase 3 Exploratory Objectives except 1 endpoint from Phase 2 Secondary Objective as noted below.

- Assess changes at 6 weeks in tumor glucose metabolism, density, and size using ¹⁸F-fluorodeoxyglucose-positron emission tomography (FDG-PET) and computed tomography (CT) (diagnostic) (Phase 2 Secondary Objective).

• CCI

•

•

•

•

•

•

•

•

•

The Phase 3 Per-Protocol Population (Ph3-PP) definition was modified. Please refer SAP section 3.1.1 for the definition.

1.8. STATISTICAL MODIFICATIONS MADE IN THE STATISTICAL ANALYSIS PLAN

Changes to Version 1.0

Changes throughout the document include minor editorial changes.

- Increase the number of enrolled patients in the Phase 3 portion of the study based on protocol version 8.0 dated 30 January 2020.
- Time-to-progression (TTP) was changed from a key secondary endpoint to a secondary efficacy endpoint. In sensitivity analysis for OS, the two-stage estimation method will be implemented to assess the impact of cross-over on the effect of selinexor on OS based on protocol version 9.0 dated 21 May 2020.
- Add more details to the TEAE definition

2. GENERAL STATISTICAL METHODS AND DATA HANDLING

This statistical analysis plan (SAP) outlines the methods to be used in the analysis of clinical data in order to answer the study objectives. Populations for analysis, data handling rules, and statistical methods are provided. This SAP does not include endpoints and methods to be used in the analysis of CCI [REDACTED]; these will be included in a separate plan.

2.1. GENERAL ANALYSIS METHODS

This is a multicenter randomized double-blind Phase 2-3 study. All summary statistics will be computed and displayed among the corresponding analysis population, and by each scheduled assessment time point whenever applicable. Summary statistics for continuous variables will minimally include n, median, mean, standard deviation, minimum, and maximum. For categorical variables, frequencies and percentages will be presented. For time-to-event variables, the Kaplan-Meier method will be used for descriptive summaries. Graphical displays will be provided as appropriate.

Data from phase 2 and phase 3 will be presented separately.

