14.2.3. Safety Population

The safety population will consist of all patients who have received any amount of study treatment. Patients will be analyzed according to the treatment actually received.

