14.3.6. Safety Analysis

Safety analyses will be performed on the Safety Population, which includes all patients who receive at least one dose of study treatment. Patients will be analyzed according to the treatment actually received.

Phase 2 safety data will be integrated with the Phase 3 safety data in the final safety analysis.

The safety and tolerability of selinexor will be evaluated by means of drug-related AE reports, physical examinations, and laboratory safety evaluations. CTCAE, v.4.03 will be used for grading of AEs. Investigators will provide their assessment as either related or not related to study treatment.

TEAEs, SAEs, AEs of at least Grade 3 in severity, related AEs, and AEs leading to withdrawal of treatment will be summarized by treatment group and in the overall safety population. TEAEs will be those that start or worsen on or after the first day of study treatment, through 30 days after last dose; related AEs will be those with an Investigator determination of related to treatment. Laboratory data will be analyzed by summary statistics over time, as well as by shift tables based on CTCAE v. 4.03 grades of severity.

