3.1.2. Safety Populations

For evaluation of safety, the following safety populations are defined:

- The ***Phase 3 Safety Population (Ph3-SAF)*** will consist of all patients in Phase 3 who have received at least one dose of blinded study treatment.
- The ***Phase 2 Safety Population (Ph2-SAF)*** will consist of all patients in Phase 2 who have received at least one dose of blinded study treatment.

Patients in safety populations will be analyzed according to the actual treatment received.

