5. SAFETY

Safety analyses will be reported by the actual treatment arm patients received and overall, among the Ph3-SAF and Ph2-SAF populations respectively. Unless otherwise specified, only data from the blinded treatment period will be presented. Please refer to Section 2.4 on definitions of observation periods.

For patients in the Ph3-OL and Ph2-OL populations respectively, selected safety data from the open-label period will be presented in separate summaries.

Safety analyses will be based on the reported AEs and other safety information, such as 12-lead electrocardiogram (ECG), vital signs, physical examination, ECOG performance status, clinical laboratory assessments including hematology and serum chemistry.

General rules

All safety analyses will be performed using the following common rules:

- Safety data in patients who do not belong to the safety population (e.g., enrolled but did not receive any dose of study treatment, partial or complete) will be listed separately.
- The baseline value is the last available value before first dose of study treatment. Please refer to Section 2.6 for details.
- The analyses of the safety variables will be essentially descriptive with no systematic testing planned.

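### The SAP reports safety only by phase and does not list this as a change, so the integrated Phase 2 and Phase 3 safety analysis specified in the protocol would not be delivered

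*SAP*

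**What the plan says.** The protocol makes the commitment twice, in the Statistical Methods part of the synopsis and in 14.3.6: "Phase 2 safety data will be integrated with the Phase 3 safety data in the final safety analysis". In the synopsis it comes directly after the statement that Phase 2 is left out of the final efficacy analysis, so safety is deliberately treated differently. Protocol 14.2.3 defines a single safety population without regard to phase: "The safety population will consist of all patients who have received any amount of study treatment".

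The SAP takes the other course throughout:

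- SAP 2.1, as a general rule with no exception for safety: "Data from phase 2 and phase 3 will be presented separately".
- SAP 3.1.2 defines Ph3-SAF, which "will consist of all patients in Phase 3 who have received at least one dose of blinded study treatment", and Ph2-SAF, which "will consist of all patients in Phase 2 who have received at least one dose of blinded study treatment". No third, combined set is defined.
- SAP 3.1.3 defines the open-label populations by phase as well (Ph3-OL and Ph2-OL).
- SAP 5 reports safety "among the Ph3-SAF and Ph2-SAF populations respectively". For the open-label populations, "selected safety data from the open-label period will be presented in separate summaries".

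SAP 1.7 is the section that records departures from Protocol v9.0. Besides endpoints dropped because their data are unavailable, its readable content is that "The Phase 3 Per-Protocol Population (Ph3-PP) definition was modified". SAP 1.8 mentions safety only in connection with the TEAE definition.

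**The concern.** The two documents cannot both be followed. A programmer working from the SAP would produce two parallel sets of safety tables and nothing that answers the protocol's commitment. A reader who checked SAP 1.7 for departures would not learn that this analysis had gone.

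The protocol's reason for separating the phases is specific to efficacy: the response criteria moved from WHO to RECIST v. 1.1. That has no direct bearing on how adverse events are graded or tabulated. Both phases use 60 mg twice weekly against matching placebo, one schedule of assessments (protocol Table 1) and CTCAE v. 4.03. The SAP gives no reason of its own for the separation.

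What is at stake is delivery of a protocol-specified analysis and a single selinexor rate for each event. The latter is most useful for uncommon AECI categories such as sepsis, cataract and neurological toxicity (SAP Table 5-1). The primary endpoint and its type I error are not touched.

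**Working it through.** **Counts.** SAP 1.1 gives 342 randomized, and this reproduces: 57 (Phase 2) + 285 (Phase 3) = 342. The protocol synopsis gives Phase 2 arms of 27 selinexor and 30 placebo, and 27 + 30 = 57. Actual Phase 3 arm sizes are not stated. From the 2:1 allocation, 285 × 2/3 = 190 selinexor, leaving 95 placebo. All of these are randomized counts; treated counts are not given.

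**Combined blinded set.** Selinexor 27 + 190 = 217; placebo 30 + 95 = 125. Phase 3 supplies 190/217 = 88% of the selinexor patients.

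**Precision with and without Phase 2.**

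- 95% upper bound for an event seen in no patient, 1 − 0.05^(1/n): n = 190 gives 1.56%; n = 217 gives 1.37%.
- 95% half-width at a 10% rate, 1.96 × √(0.1 × 0.9/n): n = 190 gives 4.3 points; n = 217 gives 4.0 points.
- Phase 2 alone, n = 27: upper bound 10.5%, half-width 11.3 points.

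**Sensitivity to the derived 190.** With the planned 185 the combined group is 212. The upper bound then moves from 1.61% to 1.40%, and the half-width still moves from 4.3 to 4.0 points.

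**Effect of unequal allocation.** In a crude pool, Phase 2 would supply 27/217 = 12.4% of selinexor patients but 30/125 = 24.0% of placebo patients. Suppose an event has no treatment effect but has rate p2 in Phase 2 and p3 in Phase 3. The crude selinexor rate is p3 − 0.124(p3 − p2), and the crude placebo rate is p3 − 0.240(p3 − p2). The spurious difference between arms is 0.116(p3 − p2), roughly one eighth of any gap between the phases. This is a reason to stratify a comparison of arms by phase. It is not a reason to omit the integration.

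**The case against.** Four points can be made for the SAP.

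**Nothing goes unreported.** TEAEs in both phases are tabulated, all SAEs and deaths are listed, and open-label data have their own summaries. A reader might infer that splitting the tables lowers the chance of seeing a rare toxicity. The documents do not support that. Whether a case is seen depends on how many patients are treated and followed, not on whether the tables are combined; a sepsis case among the 27 Phase 2 patients appears either way. Only the precision of a combined rate changes. This point stands.

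**The main table is not small.** A reader might also infer that selinexor exposure is scattered over small tables. That describes Phase 2 (27), Ph2-OL (at most 30) and, less so, Ph3-OL (at most 95). It does not describe the Phase 3 table of about 190. This stands too.

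**The phases differ in more than allocation.** Phase 2 stratified on 1 versus 2 or more prior therapies, whereas Phase 3 patients needed at least 2. Protocol Figure 1 shows that Phase 2 patients under versions up to 3 were unblinded on WHO progression, and protocol 5.2 says those criteria called progression early (48 WHO events against 28 by RECIST v. 1.1). Blinded exposure in Phase 2 may therefore have been shorter. This is a fair reason to keep the by-phase tables, but the SAP does not give it, and the protocol chose integration after the change of criteria.

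**The change may be recorded elsewhere.** The blacked-out bullets in SAP 1.7 follow a lead-in limited to endpoints not analysed for lack of data, so they are an unlikely place for it. A separate integrated safety plan cannot be excluded, but the SAP cites none. Nor is it a matter of timing: SAP 1.6 covers the end-of-study analysis as well as the primary one.

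**Conclusion.** The inconsistency is real, and the SAP does not disclose it. As written, the SAP does not deliver the integrated safety analysis that the protocol specifies, and it gives no combined selinexor rate.

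The statistical consequence is modest: about 190 versus about 217 patients, a zero-event upper bound of 1.56% versus 1.37%, and a half-width at a 10% rate of 4.3 versus 4.0 points. These figures assume that Phase 3 split exactly 2:1 and that randomized counts stand in for treated counts.

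A reader might go further and take the protocol as promising a set of everyone ever exposed to selinexor, crossovers included. The wording does not reach that far: it commits to integrating Phase 2 with Phase 3 and does not say that open-label crossover exposure will be pooled with the randomized selinexor arm. The number of crossovers is not stated either. This is a minor point, worth correcting because the analysis was specified in the protocol and is cheap to supply.

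**What to change.** Add to SAP 3.1.2 an integrated safety population: all Phase 2 and Phase 3 patients who received at least one dose of blinded study treatment, analysed by treatment received and under the treatment-period rules already in SAP 2.4. Add to SAP 5 descriptive tables on that population for TEAEs, SAEs, deaths and AECIs. Amend the sentence in SAP 2.1 so that it allows this exception. Keep the by-phase tables.

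Stratify any between-arm comparison by phase, or show it with the phases side by side, because of the 12% versus 24% imbalance. No hypothesis testing is needed, which fits the descriptive approach in protocol 14.3.6.1 and SAP 5.

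An all-selinexor set that includes crossovers would be a useful option, but it goes beyond the protocol's commitment. If the sponsor prefers not to integrate, SAP 1.7 should at least state the omission and the reason; that would cure the non-disclosure but not supply the analysis.

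The cost is SAP wording plus a few extra tables to program and review. No new data are required.

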2.2. MISSING DATA HANDLING IN DATA PRESENTATION

In general, missing baselines will not be imputed. The following approaches are default methods for missing data handling in summary tables.

- Categorical data at baseline will be summarized using counts (n) and percentages (%). Denominator will be the analysis population specified for the summary, unless otherwise specified. Missing data may be presented as a separate category.
- Continuous data: summaries will be based on observed data only.

2.2.1. Handling of Computation of Treatment Duration if Study Treatment End of Treatment Date is Missing

For the calculation of treatment duration, the date of the last dose of study treatment is equal to the date of last study treatment dosing reported on study treatment dosing form. If all the dosing dates are missing, then the duration is missing.

The last dose intake should be clearly identified on the eCRF dosing page and should not be approximated by the last returned package date.

2.2.2. Handling of Missing/Partial Dates for Adverse Events or Concomitant Medications

In general, the imputation should be conservative such that onset dates should be imputed to be as early as possible and resolution dates will be imputed to be as late as possible. Impute resolution date first and then impute onset date using imputed resolution date. However, for categorization purpose, if the partial AE onset date information does not indicate whether the AE started prior to treatment or after the treatment-emergent adverse event (TEAE) period, the AE will be classified as treatment-emergent. Handling of missing or partial dates for AE or concomitant medications will consider the start date of selinexor for patients who cross over from placebo to open-label selinexor.

These data imputations are for categorization purpose or calculation of AE duration, and will not be used in listings. In data listings, an ongoing flag will be identified from the eCRF AE page.

Refer to *Karyopharm Biostatistics and Statistical Programming Rule Book* v2.0 for details on imputation methods.

2.2.3. Handling of Missing or Partial Birth Date for Calculation of Age

Refer to *Karyopharm Biostatistics and Statistical Programming Rule Book* v2.0 for details on imputation methods.

2.2.4. Handling of AEs When Date and Time of First Dose of Study Treatment Are Missing

When the date and time of the first dose of study treatment are missing, all AEs that occurred on or after signing the informed consent should be considered as TEAEs. The exposure duration should be kept as missing.

2.2.5. Handling of Missing Assessment of Relationship of AEs to Study Treatment

If the assessment of the relationship to study treatment is missing, then the relationship to study treatment in the frequency tables is considered as possibly related.

2.2.6. Handling of Missing Severity of AEs

If the severity is missing for one of the treatment-emergent occurrences of an AE, the maximal severity on the remaining occurrences will be considered. If the severity is missing for all the occurrences, a “missing” category will be added in the summary table.

2.2.7. Handling of Missing Data in Patient-Reported QoL Measurements

For patient-reported QoL measurements, missing data will be handled as described in the EORTC-QLQ-C30 and EQ-5D-5L scoring manuals.

2.3. STUDY TREATMENT DOSING DATE

Study treatment dosing date is the date on which a patient actually received study treatment (selinexor or placebo, partial or complete).

For blinded treatment,

- Except for few patients who were randomized to selinexor in blinded treatment and entered open-label phase, the date of first study treatment is defined as the earliest date of non-zero dose of either selinexor or placebo. The date of last study treatment is defined as the latest date of non-zero dose of either selinexor or placebo before end of blinded treatment.
- For patients who were randomized to selinexor in blinded treatment and entered open-label phase, the date of first study treatment is defined as the earliest date of non-zero dose of selinexor, the date of last study treatment is defined as the latest date of non-zero dose of selinexor, regardless of blinded or open-label phase.

For open-label treatment, the date of first study treatment is defined as the earliest date of non-zero dose of open-label selinexor. The date of last study treatment is defined as the latest date of

non-zero dose of open-label selinexor. This definition only applies to patients who were randomized to placebo in blinded treatment and entered open-label phase.

2.4. OBSERVATION PERIOD

For the patients who do not enter open-label selinexor, the observation period will be divided by the following:

- The pre-treatment period is defined as the time since the signed informed consent date up to the time before the date of first blinded study treatment.
- The blinded treatment period is defined as the time from the date of first blinded study treatment up to the date of last blinded study treatment + 30 days inclusive, or the day before initiation of a new anti-neoplastic treatment, whichever occurs first.
- The post-treatment period is defined as the time beyond the blinded treatment period.

For the patients who were randomized to placebo in blinded phase and entered open-label selinexor, the observation period will be divided by the following:

- The pre-treatment period is defined as the time since the signed informed consent date up to the time before the date of first blinded study treatment.
- The blinded treatment period is defined as the time from the date of first blinded study treatment up to the date of last blinded study treatment + 30 days inclusive, or the date of first open-label study treatment exclusive, whichever occurs first.
- The open-label treatment period is defined as the time since the date of first open-label study treatment to the date of last open-label study treatment + 30 days inclusive, (or the day before initiation of a new anti-neoplastic treatment, whichever occurs first).
- The post-treatment period is defined as the time beyond the open-label treatment period.

For the few patients who were randomized to selinexor in blinded phase and entered open-label selinexor, the observation period will be divided by the following:

- The pre-treatment period is defined as the time since the signed informed consent date up to the time before the date of first study treatment.
- The blinded treatment period is defined as the time from the date of first study treatment up to the date of last study treatment + 30 days inclusive, or the day before initiation of a new anti-neoplastic treatment, whichever occurs first. Please note that open-label selinexor is not considered a new anti-neoplastic treatment here.
- The post-treatment period is defined as the time beyond the blinded treatment period.

Please refer to Section 2.3 for the definitions of dates of first and last study treatment.

2.5. STUDY DAY CALCULATION

Based on the study protocol, study Day 1 is the first study treatment dosing date in blinded treatment period. The day before Day 1 is considered Day -1, there is no Day 0.

The study day in open-label selinexor will also be calculated using the start date of open-label selinexor treatment as reference point. For example, the first dose date of open-label selinexor will be referred as open-label Day 1 or OL Day 1.

A patient is considered as treated in a cycle if the patient received any non-zero dose of either selinexor or placebo in that cycle.

Study day for a given assessment is defined as

- the assessment date – the date of first study treatment + 1 if the assessment date is on or after Day 1, or
- the assessment date – the date of first study treatment if the assessment date is before Day 1.

2.6. BASELINE MEASUREMENT

For blinded treatment period, the baseline value is defined as the latest value prior to the first dose of blinded study treatment. In the case an assessment performed on the same date as the first dosing date, but it is impossible to determine the evaluation time relative to the time of taking the first dose, the evaluation time will be assumed to be following the protocol-defined schedule.

For patients who proceed to open-label period, the baseline value for assessments in open-label treatment period will be the latest value prior to the date of first open-label study treatment.

